1. ABSTRACT/STUDY DIAGRAM

Most cocaine dependent patients suffer from deficits in cognitive function that, if left untreated, predict poor outcome.

Purpose: The present study investigates a pharmacotherapeutic intervention designed to improve cocaine treatment success by combining medications that act simultaneously on dopamine, the brain system that is critically associated with chronic cocaine use and cognitive functions. **Procedures:** Treatment with levodopa/carbidopa plus ropinirole (tested at two doses) will be compared to levodopa/carbidopa alone, and placebo. Measurement of performance on behavioral/cognitive measures of decision-making, behavioral inhibition, reward motivation, and attentional bias will be conducted at treatment entry and at repeated time points during the 10-week treatment. It is hypothesized that treatment with levodopa/carbidopa + ropinirole will produce superior outcomes in terms of reduced cocaine use and increased treatment retention and that these effects will occur indirectly via improved performance on observed cognitive mechanisms. **Course of Study:** Eligible cocaine dependent patients will be randomized equally to one of four medication conditions. Outpatient treatment will last 10 weeks and consist of thrice-weekly clinic visits. The behavioral therapy platform for this trial will consist of weekly cognitive behavioral therapy (CBT). The primary outcome measure will be weekly mean proportion of cocaine non-use days. Secondary endpoints will include abstinence rates during the last 2 weeks of treatment, time in study, and medication compliance. **Enrollment:** This project requires a final intent-to-treat sample size of 200 subjects. To obtain this sample, we expect to conduct phone screens on ~ 640 individuals, of whom 320 (50%) will qualify, enroll, and start intake. Of the 320 who start intake, we expect that 200 (~60%) will complete intake and be randomized into the ITT sample. Based on these projections and recruitment rates achieved during our previous levodopa studies, 40 months will be allotted to complete study enrollment (~ 5 new subjects/month).

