6.2 STUDY DRUG #2

Ropinirole. The drug, ropinirole, is a DA (primarily type D₂ and D₃) receptor agonist used in the treatment of Parkinson's disease. Preliminary studies suggest that ropinirole is safe, and may reduce cocaine use. In an open-label trial (Meini et al., 2008), 39 subjects with cocaine dependence received ropinirole at 1.5 mg/day for 12 weeks. Average rates of benzoyllecgonine-positive urines decreased from 90.2% at baseline to 17.8% at week 6. Twelve subjects achieved sustained cocaine abstinence for up to 10 weeks.

Participants assigned to a medication combination condition will also receive ropinirole in the extended-release formulation (REQUIP XLTM), with a one-week dose titration schedule to reach fixed dose levels of 2.0 mg/d or 4.0 mg/d, depending on study condition. These doses were chosen based on a previous study of ropinirole in cocaine dependence and dosage titration recommended for Parkinson's disease to minimize risk of side effects (REQUIP XLTM prescribing information) (see titration schedule, below).

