Cognitive-enhancing DA Medications for Cocaine Dependence

NCT01393457

Version Date: 09/02/2011

STATISTICAL ANALYSIS PLAN (SAP)

Data will be entered by research assistants into an existing, relational database (i.e. Microsoft Access). Data integrity will be maintained by restricting allowable input values on standardized Access entry forms. Double entry of a random subset of 10% of the observations will be used to identify problematic data entry issues. Preliminary data analyses evaluating group differences on demographic and baseline variables will use contingency tables with chi-square testing, ANOVA's, and examination of correlations between baseline variables and specified outcomes. Baseline or demographic variables, on which group differences are detected and which are correlated with outcomes, meet the definition of confounders and will result in two sets of analyses: one in which the relevant variable is included as a covariate and one in which it is not. This will permit determination of the degree to which any group differences might confound conclusions regarding treatment.

Broadly, the data analytic strategy will use generalized linear modeling and mixed effects models. Longitudinal analyses will be conducted using generalized linear mixed modeling (Proc GLIMMIX; SAS 9.2) for both continuous and discrete outcomes. Count, dichotomous and time to event data will be evaluated using Poisson (Proc GENMOD; SAS 9.2), logistic (Proc GENMOD; SAS 9.2), and proportional hazards regression (Proc PHREG; SAS 9.2) respectively. Distributional assumptions will be evaluated via inspection of residual plots and, where possible, by formal statistical tests. Violation of assumptions will be addressed, depending upon statistical technique, through the use of transformations, robust estimators, scaling coefficients, and stratification. Sample size approximations are obtained through empirical data simulation using SAS v.9.2.

PRIMARY HYPOTHESIS TESTING: To evaluate the efficacy of combination levodopa/carbidopa-ropinirole therapy in treatment of cocaine dependence. H1. The combination of levodopa/carbidopa and ropinirole will reduce cocaine use and increase treatment retention. H2. There will be a dose-response relationship such that

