 $[\text{levodopa}/\text{carbidopa} + 4 \text{ mg/d ropinirole}] > [\text{levodopa}/\text{carbidopa} + 2 \text{ mg/d ropinirole}] > [\text{levodopa}/\text{carbidopa} + \text{placebo}] > [\text{placebo} + \text{placebo}]$. H1 will test for differential change over time as a function of treatment. H2 will test the ordinal relations of treatment effects as a follow-up analysis. As defined above (see Sect. B.3.2.5.ii) cocaine use will be measured by urine benzoylecgonine and by the SPRHK1 approach. Generalized linear mixed models will evaluate the probability of cocaine use as a function of time, treatment and their interaction. Logistic regression will evaluate retention, defined by completion of 12 weeks of treatment, as function of intervention condition. Proportional hazards regression will evaluate time to drop-out as a function of treatment. If differential attrition raises concerns regarding non-ignorable missingness, evaluation of cocaine use will implement pattern-mixture modeling. To evaluate the relative efficacy of the treatment conditions we will follow up the omnibus test with ordinal contrasts.

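### The SAP counts a participant as retained only after 12 weeks of treatment, but the protocol provides 9 or 10, so there can be no completers and the logistic model cannot be fitted

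*SAP*

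**What the plan says.** Under primary hypothesis testing, the SAP states H1 as "The combination of levodopa/carbidopa and ropinirole will reduce cocaine use and increase treatment retention". It gives retention two analyses. The first is binary: "Logistic regression will evaluate retention, defined by completion of 12 weeks of treatment, as function of intervention condition". The second is time-based: "Proportional hazards regression will evaluate time to drop-out as a function of treatment". Cocaine use is handled separately: "Generalized linear mixed models will evaluate the probability of cocaine use as a function of time, treatment and their interaction".

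The protocol describes a shorter trial. Section 1 states: "Outpatient treatment will last 10 weeks and consist of thrice-weekly clinic visits". The dosing tables in section 6.4 stop at week 10, labelled run-down, and the schedule in section 8 also ends at week 10. Section 7.2.3, however, describes a treatment phase of 9 weeks, and section 7.2.5 places the end-of-study visit at week 9.

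Section 1 also names the outcomes. For the primary: "The primary outcome measure will be weekly mean proportion of cocaine non-use days". For the rest: "Secondary endpoints will include abstinence rates during the last 2 weeks of treatment, time in study, and medication compliance".

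**The concern.** A completer is defined by a length of treatment that nobody in the trial is offered. If the rule is applied literally, every participant is a non-completer, the outcome is constant, and one of the two planned tests of the retention half of H1 yields nothing.

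The number must therefore be replaced, and the protocol does not settle by what. Someone who attends through week 9 and then stops is a completer under sections 7.2.3 and 7.2.5 and a drop-out under section 1. The SAP does not say which, nor at which week time to drop-out is censored. If that is left open until the data are unblinded, the definition can be chosen with the results in view.

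The abstinence endpoint inherits the problem, because its window is the last two weeks of a treatment period whose end is not fixed.

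**Working it through.** **Durations side by side**

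| Source | Length or last week |
|---|---|
| SAP, retention definition | 12 weeks |
| Protocol 1, abstract | 10 weeks |
| Protocol 6.4, dosing tables, all four arms | week 10 (run-down) |
| Protocol 8, assessment schedule | week 10 |
| Protocol 7.2.3 | 9 weeks |
| Protocol 7.2.5, end-of-study visit | week 9 |
| Protocol 6.5, Table 1 | draws entered for weeks 1–9 only |

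The only other 12-week treatment length in the documents belongs to a cited open-label study in section 6.2: "39 subjects with cocaine dependence received ropinirole at 1.5 mg/day for 12 weeks".

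**Table 1 reproduced.** Draws per visit equal the week number, with three visits a week and 5 bonus draws a week:

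- Weeks 1–9: 3 × (1 + … + 9) + 9 × 5 = 135 + 45 = 180, the stated total.
- The same pattern for 10 weeks: 3 × 55 + 50 = 215.
- For 12 weeks: 3 × 78 + 60 = 294.

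The total of 180 is therefore a 9-week figure.

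**Completers under the SAP's rule.** Section 1 gives 200 participants randomized equally to four arms: 200 / 4 = 50 per arm. The longest treatment is 10 weeks, and 10 < 12, so completers are 0/50 in each arm and 4 × 0 = 0/200 overall. In visits, 12 weeks would need 12 × 3 = 36. The plan schedules 10 × 3 = 30 or 9 × 3 = 27, so the rule asks for 6 or 9 visits that do not exist.

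**What the logistic model does with this.** With no events, the log-likelihood is the sum over arms of 50 × log(1 − p), which increases as each p falls to 0. The log-odds run to minus infinity and there is no finite maximum. Any odds ratio between arms is (0/50) / (0/50), which is undefined. A trial fit on 200 zeros in four arms produced a perfect-separation warning. The standard errors it printed (about 43,200 for the arm terms in one fit, above 100,000 in another) reflect where the iterations stopped and are not estimates.

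**With a reachable cutoff.** The documents give no retention rate, so one must be assumed. If about half of each arm is retained, the standard error of a log odds ratio between two arms is √(2 / (50 × 0.5 × 0.5)) = √0.16 = 0.40. Simulated data with 43–55% retained gave 0.40–0.41. This shows only that the model becomes estimable; it is not a power statement.

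**The last-two-weeks window.** Three urine visits a week give 6 visits in either reading.

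- Weeks 9–10: the 3 visits of week 10 fall in the run-down, 3/6 = 50%.
- Weeks 8–9: 0/6.

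Scheduled daily doses in week 10 (section 6.4) are:

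| Arm | Levodopa/carbidopa | Ropinirole |
|---|---|---|
| Placebo | 0 | 0 |
| Levodopa/carbidopa alone | 400/100 mg | 0 |
| With ropinirole 2 mg | 400/100 mg | 0 |
| With ropinirole 4 mg | 400/100 mg | 2 mg |

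The second and third rows are identical, so four arms have three distinct regimens that week. One of the dose steps ordered in H2 is absent for half of a weeks 9–10 window.

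**The case against.** The strongest reply is that 12 is a carried-over number. The intent, completing the planned treatment, is plain, and a first run would expose the error at once. Table 1 supports carry-over: it has columns for weeks 11–13 and numbers visits up to 39. Those columns hold no draws, and nothing else in the protocol schedules dosing or assessments that late, so they do not rescue the definition. The intent does not supply the replacement number either.

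It can also be said that 9 and 10 reconcile as nine weeks of treatment plus a run-down week. That is a sensible reading, but the documents do not state it, and the abstract counts all ten weeks as treatment. The evidence is mixed even within sections: section 8 marks prize draws, urine tests and a closing depression inventory in week 10, while the end-of-study visit and the last cognitive tests are in week 9.

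Three further points have some force:

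- Time to drop-out by proportional hazards still tests retention. This is correct, and it is the main limit on the harm. Censoring completers at their last scheduled contact would work, but that contact is in week 9 or week 10 depending on the section.
- Section 7.2.1 conceals assignment from everyone except the pharmacist. This protects a choice made before unblinding, not one made afterwards.
- The primary outcome is untouched by the 12-week rule, but whether week 10 enters the cocaine-use model depends on the same unsettled length. That is a fair qualification, and one more reason to fix the length.

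**Conclusion.** The concern holds. As written, the binary retention analysis has 0 of 200 completers and cannot be estimated. This rests only on the documents' own durations and on applying the SAP's definition literally.

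The consequence is moderate. One of two retention analyses under H1 fails, the other survives without a stated censoring week, and the primary cocaine-use outcome does not depend on the 12-week cutoff. How far the choice of week 9 or week 10 would move the difference between arms, or the power, is unknown in size and direction because no retention rates are given. The window for the abstinence endpoint is a secondary consequence: between 0 and 3 of its 6 visits fall in the run-down, depending on the reading.

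**What to change.** Before unblinding:

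1. Replace 12 weeks in the SAP with a single completion week, and make the treatment length agree throughout both documents.
2. Prefer week 9: it has the end-of-study visit, the last maintenance doses and the last cognitive tests. Report week 10 as a sensitivity analysis. Week 10 as the main definition is also acceptable, since urine tests are scheduled then.
3. Censor time to drop-out at the chosen week.
4. Name the two weeks that make up the end-of-treatment abstinence window. Weeks 8–9 keep the run-down out; scheduled doses are then at maintenance, apart from the permitted hold of the 4 mg arm at 2 mg.
5. State whether week 10 enters the cocaine-use model.

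The cost is wording in the SAP and protocol. No participants, visits or staff are added.

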7.2.4 EARLY TERMINATION

Premature termination of a subject from the study will be considered clinically appropriate for any of the following reasons: (1) significant side effects from the study medication; (2) serious or unexpected AEs; (3) inability to comply with the study protocol; (4) protocol violation; or (5) emergence of serious medical or psychiatric illness.

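### The only check for non-ignorable drop-out depends on differential attrition, yet similar attrition across arms does not make drop-out ignorable

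*SAP*

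**What the plan says.** All the relevant analysis text is in the SAP's primary hypothesis testing paragraph.

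- Main test: "H1 will test for differential change over time as a function of treatment". The model: "Generalized linear mixed models will evaluate the probability of cocaine use as a function of time, treatment and their interaction".
- Attrition analyses, both planned unconditionally: "Logistic regression will evaluate retention, defined by completion of 12 weeks of treatment, as function of intervention condition" and "Proportional hazards regression will evaluate time to drop-out as a function of treatment".
- The only provision for non-ignorable missingness: "If differential attrition raises concerns regarding non-ignorable missingness, evaluation of cocaine use will implement pattern-mixture modeling". No test, threshold or identifying restriction is attached to it.
- Outcome scoring: "cocaine use will be measured by urine benzoylecgonine and by the SPRHK1 approach", with a pointer to Sect. B.3.2.5.ii, which is not part of the supplied text.

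The Protocol adds three facts. Section 1 states "Outpatient treatment will last 10 weeks and consist of thrice-weekly clinic visits", while section 7.2.3 (In Treatment) describes a 9-week phase. Urine is collected at clinic visits (sections 7.2.3 and 8), and the supplied text describes no collection after early termination. The Early Termination section lists among its reasons "1) significant side effects from the study medication; (2) serious or unexpected AEs; (3) inability to comply with the study protocol". Neither attrition analysis in the SAP uses these reasons.

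**The concern.** The two sentences before the conditional one model retention and drop-out by treatment, so differential attrition most naturally means attrition that differs by arm. That is the wrong thing to look at. A likelihood-based mixed model is protected when leaving can be explained by data already observed. Comparing the numbers who leave says nothing about that. Two arms can each lose 40%, one for reasons unrelated to use and the other because patients relapse and stop coming.

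At stake is the cocaine-use comparison, the trial's primary efficacy question. Under the rule as written, a missing-at-random contrast could be reported with no sensitivity analysis because the arms lost similar numbers. Depending on which arm has the use-related drop-out, a benefit could be created or hidden. If the condition is met instead, the reader cannot tell which of two models is the main analysis, and that choice is made after attrition has been seen.

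**Working it through.** **Inputs from the documents.** 200 randomized equally to four arms: 200/4 = 50 per arm. Treatment lasts 10 weeks, with an end-of-study visit at week 9 (Protocol 7.2.5). No drop-out rate, alpha, power or effect size is given, so there is no figure of the plan's own to reproduce. All attrition rates and mechanisms below are assumptions.

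**Step 1: what attrition counts cannot show.** With attrition d in both arms, the true arm mean = (1 − d) × completer mean + d × leaver mean. Let g be leaver mean minus completer mean in an arm. Then

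true contrast − completer contrast = d × (g of arm 1 − g of arm 2).

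If the gaps differ by 0.20: 0.2 × 0.20 = 0.04; 0.4 × 0.20 = 0.08; 0.6 × 0.20 = 0.12. If the gaps are equal, the result is 0. A mixed model also uses leavers' earlier data, so its bias needs simulation.

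**Step 2: drop-out depending on current unobserved use.** Random-intercept logistic model with week, arm and interaction; 10 weekly binary outcomes; two arms of 400; 60 replicates; 40% attrition in each arm; no true effect. The log-odds of leaving shift by 2 when the patient is using. Week-10 difference, treated minus control (Monte Carlo SE about 0.004):

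| Mechanism | Estimate |
|---|---|
| Unrelated to use in both arms | 0.004 |
| Users leave more, both arms | 0.002 |
| Users leave more, treated only | −0.046 |
| Users leave more, control only | +0.040 |
| Opposite mechanisms in the two arms | −0.093 and +0.086 |

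**Step 3: drop-out at a jump in use.** In every arm a share of patients has use rising from 50% to 90% at a week drawn from 2 to 10. In one arm leavers go at the jump; in the other the same number leave at random with the same timing. The true difference is within 0.7 points of zero. Size of the false week-9 difference, in points; where the process is in one arm only, that arm looks better:

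| Attrition | 20% | 40% | 50% |
|---|---|---|---|
| All leavers in one arm, jump unobserved | 7.1 | 14.3 | 17.2 |
| Same, one elevated week observed first | about 4 | 9–10 | about 11 |
| Half of leavers | 3.4 | 5.8 | 7.3 |
| A quarter of leavers | 1.3 | 3.3 | 3.0 |
| Same process in both arms | 0.8 | 0.3 | 0.4 |

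Averaged over weeks 1–9, the first row is about half as large (3.7, 7.1, 8.7).

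**Step 4: effect on the H1 test.** Four arms of 50, 800 null trials, 3-df treatment-by-time test. Cut-offs were recalibrated so that random drop-out rejects 5%. At 40% attrition, with half of leavers affected, rejection is 8.6% (process in the three drug arms) or 11.0% (in placebo). In the extreme case it is 26.8% or 30.0%, and with the same process in all arms 2.9%.

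**Step 5: would the condition be met?** The SAP names no test. If it were a two-sided 5% comparison of two arms of 50, then power = Φ[(|p1 − p2| − 1.96√(2p̄q̄/50)) / √(p1q1/50 + p2q2/50)], where q = 1 − p and p̄ is the average of p1 and p2. For 50% v 60% retention: (0.10 − 0.195)/0.099 = −0.96, power 17%. For 50% v 70%: (0.20 − 0.192)/0.096 = 0.08, power 53%. Real imbalance can be missed too. The logistic retention analysis gives no signal: nobody can complete 12 weeks of a 10-week treatment, so completion is zero in every arm.

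**Step 6: would the named method help?** In the first-row scenario of Step 3, a pattern-mixture model (early, late, completer; leavers' own level, completers' slope) gave 7.1, 14.8 and 17.4 points, so it removed none of the bias. A shift of 39 to 42 points in that arm's post-drop-out use closed the gap. No observed data can supply that shift.

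**The case against.** The strongest reply has four parts.

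- H1 itself predicts better retention on the combination, and time to drop-out is analysed unconditionally. If H1 is right, the condition may well be met, and the blind spot needs similar timing as well as similar numbers. This stands and narrows the gap. It does not cover the case where arms lose similar numbers at similar times.
- All arms share the same therapy, attendance prizes, matched capsules and concealed assignment, so similar drop-out processes are plausible, and the bias is then about zero. This also stands. Differing processes are possible, since side effects and inability to comply are listed reasons for termination, but the documents give no rates by arm. A reader might infer that the trial's contrast is biased, or biased toward the drug. The documents support neither.
- The largest figures are upper-end. They need every leaver in one arm to go at a jump that no urine sample captures, although urine is tested three times a week. A reader might take 14 points or a false-positive rate near 30% as the expected damage; moderate mechanisms give much less.
- Missed urines may be scored in Sect. B.3.2.5.ii. If so, the mixed model may have little missing data and the bias figures may not describe it. A scoring rule would itself be an assumption that deserves a sensitivity analysis.

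**Conclusion.** The point holds as a gap in pre-specification, not as a demonstrated bias. Similar attrition does not establish ignorability, the condition is undefined, and the standing of the pattern-mixture model relative to the mixed model is unstated. At an assumed 40% equal attrition and no true effect, the false week-9 difference is roughly 3 to 10 points in moderate cases, about 14 in the extreme case, and about zero when the process is common to all arms. The direction depends on which arm is affected. The sizes rest on assumed mechanisms, a weekly binary outcome, and missed urines not being scored by rule. The logical gap does not depend on the sizes.

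A reader might infer that simply deleting the condition cures the problem. It does not: a pattern-mixture model identified from observed data alone left the bias in place in the case tested.

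The conflict between the 12-week retention definition and the treatment length is a separate inconsistency. It disables the logistic retention analysis but does not affect the time-to-drop-out analysis.

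**What to change.** Replace the conditional sentence with a paragraph that:

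1. States that the mixed model is the primary analysis whatever the attrition.
2. Always reports beside it an arm-specific delta-adjusted or tipping-point analysis of use after drop-out, running up to all use, and gives the shift at which the H1 treatment-by-time conclusion changes. Apply it to the urine results and to the weekly proportion of non-use days.
3. Tabulates week of drop-out and the Protocol's early-termination reason by arm.
4. Keeps pattern-mixture modeling only as an optional supplement, with a few pooled patterns and stated identifying restrictions. At an assumed 40% attrition there are 0.4 × 50 = 20 leavers per arm, about 10 per early or late pattern, so its estimates will be imprecise.
5. States how missed urines are handled, or reproduces the rule if Sect. B.3.2.5.ii already has one.

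Separately, reconcile the SAP's 12-week completion definition with the Protocol's 10-week treatment (section 1) and 9-week phase (section 7.2.3).

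Cost: one SAP paragraph and a little more analysis, with no new data and no change to sample size or alpha. The price is that a positive result may be shown to be sensitive to assumptions about drop-out.
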